9.2.1. Incidence of Adverse Events

An overview summary of the following TEAE categories will be provided:

- Any TEAE
- Any TEAE through 28 Days Following Study Vaccination Day 1
- Any TEAE related to vaccination
- Any TEAE related to MAD
- Any serious TEAE
- Any serious TEAE related to vaccination
- Any serious TEAE related to MAD
- Any AESI
- Any AESI Related to Vaccination
- Any MAAE
- Any MAAE Related to Vaccination
- Any MAAE Related to MAD
- Any TEAE leading to study discontinuation
- Any TEAE leading to death

9.2.2. Relationship of Adverse Events to Vaccination

The relationship of vaccination to TEAE will be characterized using the following criteria:

- Related: There is a reasonable possibility that the study vaccination caused the AE. Reasonable possibility means that there is evidence to suggest a causal relationship between the study vaccination and the AE.
- Not Related: There is not a reasonable possibility that the study vaccination caused the event.

Missing relationship will be counted as related to study vaccination.

All TEAEs through 28 days following first study vaccination and following re-vaccination/attenuated challenge (substudy) will be summarized by relationship to study vaccination, and by treatment group, age group and overall.

9.2.3. Severity of Adverse Event

The severity of the AE will be rated as mild, moderate, or severe using the following criteria:

- Mild: These events require minimal or no treatment and do not interfere with the subject's normal daily activity.
- Moderate: These events result in a low level of inconvenience or concern with the therapeutic measures. Moderate events may cause some interference with normal functioning.
- Severe: These events interrupt a subject's normal daily activity and may require systemic drug therapy or other treatment. Severe events are usually incapacitating.

If a subject reports multiple occurrences of a specific event, the subject will be counted only once by the maximum severity. If the severity is missing for one or more of the occurrences, the maximum severity of the remaining occurrences will be used.

All AEs through 28 days following first study vaccination and following re-vaccination/attenuated challenge (substudy) will be summarized by SOC/FMQ/PT and severity to study vaccination, and by treatment group.

9.2.4. Serious Adverse Events

An SAE is defined as any event that:

- results in death
- is immediately life threatening
- requires inpatient hospitalization or prolongation of existing hospitalization
- results in persistent or significant disability/incapacity
- is a congenital anomaly/birth defect

Important medical events that may not result in death, be life threatening, or require hospitalization may be considered SAEs when, based upon appropriate medical judgment, they may jeopardize the subject or may require medical or surgical intervention to prevent one of the outcomes listed in this definition.

Serious TEAEs will be summarized by SOC/PT, and by severity and relationship separately. Serious AEs will be summarized by detailed listing showing the event description, preferred term and system organ class, relevant dates (study vaccinations and AEs), severity, relatedness, and outcome for each event. Any SAE considered to be related to BPZE1 will be classified as a SUSAR.

A by-subject listing will be provided.

9.2.5. Medically Attended Adverse Events

A medically attended AE is defined as any unsolicited AE that leads to an unscheduled visit to a healthcare provider, or any grade 3 solicited reactogenicity event that leads to an unscheduled visit to a healthcare provider. All MAAEs will be summarized as number and percentage by SOC and PT, and by treatment groups, cross tabulated with severity and relationship separately.

A by-subject listing will be provided.

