7.4.3.3 Analyses of Secondary Safety Endpoints

The number and percentage of subjects will be summarized for each solicited AE by timepoint, severity grade, and treatment group. Additionally, solicited AEs will be analysed by taking the maximum severity through 7 days following any study vaccination to summarize the frequency and percentage of subjects reporting each local [if applicable; after IM injection only], nasal/respiratory, or systemic event. Mean response (for any measurement) and duration through 7 days following any study vaccination will be summarized daily using descriptive statistics. Solicited AEs will be reported separately following study vaccination on Day 85 in the substudy.

Adverse events will be coded by preferred term and system organ class using the latest version of MedDRA.

The following unsolicited AEs will be summarized as number and percentage of subjects reporting at least 1 event in each preferred term and system organ class and cross-tabulated by severity and relationship to study vaccination.

- All AEs through 28 days following first study vaccination and following re-vaccination/attenuated challenge (substudy) by severity and relationship to study vaccination, and by treatment group.
- All MAAEs through 84 days following first study vaccination and re-vaccination/attenuated challenge (substudy) by treatment group by severity and relationship to study vaccination, and by treatment group and time since study vaccination.
- All AESIs and SAEs through Day 169/EOS by treatment group by severity and relationship to study vaccination, and by treatment group and time since study vaccination.

Serious AEs will be summarized by detailed listing showing the event description, preferred term and system organ class, relevant dates (study vaccinations and AEs), severity, relatedness, and outcome for each event. Any SAE considered related to BPZE1 will be classified as a SUSAR.

The number and percentage of subjects with SARS-CoV-2 infections or AESIs associated with COVID-19 infection or SARs-CoV-2 vaccine-related events will be summarized, if the COVID-19 pandemic remains ongoing in the region or if there are mass vaccinations using a COVID-19 vaccine during study conduct.

The number and percentage of subjects with colonization or clearance by real-time PCR or *B. pertussis* culture following study vaccination (subsets of subjects) will be summarized over time using the methods outlined in Section 7.4.2 for proportions.

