3.2.2.5. Safety

Subjects participating in the substudy will be evaluated for safety endpoints in a separate evaluation after Day 85 re vaccination/attenuated challenge.

- Maximum daily severity during the 7 days following study vaccination (by treatment group).
- Incidence by toxicity grade during the 7 days following study vaccination (by treatment group).
- Mean response (for any measurements) and duration during the 7 days following study vaccination (by treatment group).
- All AEs through 28 days following study vaccination by severity and relationship to study vaccination (by treatment group).

- All MAAEs through 84 days following study vaccination by severity and relationship to study vaccination, and by time since study vaccination (by treatment group).
- All AESIs and SAEs through Day 169/EOS by severity and relationship to study vaccination, and by time since study vaccination (by treatment group).
- Incidence of SARS-CoV-2 infections or AESIs associated with COVID-19 disease by severity, and by time since study vaccination (by treatment group).
- *B. pertussis* clearance following study vaccination (subset of subjects at varying time points through Day 85).

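### The SAP's MAAE tables leave out the time-since-vaccination split that the secondary endpoint names, and tabulate severity and relationship only separately

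*SAP*

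**What the plan says.** The SAP's list of secondary safety endpoints (3.2.2.5) includes "All MAAEs through 84 days following study vaccination by severity and relationship to study vaccination, and by time since study vaccination" and, for the longer window, "All AESIs and SAEs through Day 169/EOS by severity and relationship to study vaccination, and by time since study vaccination". Protocol 2.2 has the same endpoints. Protocol 7.4.3.3 turns them into analyses: unsolicited events are to be "cross-tabulated by severity and relationship to study vaccination", and both the MAAE item and the AESI/SAE item end with "and by treatment group and time since study vaccination".

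The SAP's analysis sections read differently:

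- **MAAEs (9.2.5):** "All MAAEs will be summarized as number and percentage by SOC and PT, and by treatment groups, cross tabulated with severity and relationship separately". The section also plans a listing for each subject; its columns are not stated.
- **SAEs (9.2.4):** "Serious TEAEs will be summarized by SOC/PT, and by severity and relationship separately". A detailed listing also gives "relevant dates (study vaccinations and AEs), severity, relatedness, and outcome for each event".
- **AESIs (9.2.6):** time since vaccination is kept, and severity and relationship are again separate.

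SAP 9.2 says MAAEs will be summarized over 84 days after any vaccination and also through end of study. SAP Section 11 declares one change only, the added 10 to 17 years age group. SAP Section 1 says the SAP governs where it and the protocol are inconsistent.

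**The concern.** Programmed as written, 9.2.5 yields MAAE tables pooled over 84 days and through end of study. These do not deliver the endpoint that the SAP itself lists. No time intervals are defined anywhere in either document, so nothing fixes them in advance if someone later decides to produce the split.

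Timing is informative here. Protocol 3.1 describes this as the first study of BPZE1 in school-age children. Protocol 1.3.1.2 says BPZE1 clears over 28 days, in most subjects within the first two weeks. A medically attended reaction to the vaccine would plausibly fall early, while ordinary childhood illness accrues over the whole period. Pooling mixes the two.

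Separately, a safety reader will want to know how many MAAEs in each group were both severe and judged related. Two one-way tables do not give that count.

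**Working it through.** **Text comparison**

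| Element | SAP 3.2.2.5 | Protocol 7.4.3.3 | SAP 9.2.5 (MAAE) | SAP 9.2.4 (SAE) | SAP 9.2.6 (AESI) |
|---|---|---|---|---|---|
| Time since vaccination | Yes | Yes | No | Not in tables; dates in listing | Yes |
| Severity and relationship | Both named | Cross-tabulated | Separate | Separate in tables; both in listing | Separate |

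One SAP sentence could act as a catch-all: 8.3 says that, unless otherwise specified, each endpoint is summarized as described in Section 3.2. It sits in Section 8, Immunogenicity Analysis, and 9.2.5 specifies its own tables. It does not repair the gap.

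**Size of the dilution (illustration)**

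The documents give no MAAE rate, so there is no plan figure to reproduce and every rate below is an assumption.

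- Background: 30% by Day 84 at constant hazard, so B(t) = 1 − 0.70^(t/84).
- BPZE1 adds an independent 8% risk, complete by Day 14, so C(t) = 1 − (1 − B(t)) × 0.92.
- Group size: about 120 (SAP 4.1 and Table 3-1).

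| Window | Background B(t) | With early excess C(t) | Ratio |
|---|---|---|---|
| To Day 14 | 1 − 0.70^(1/6) = 5.8% | 1 − 0.942 × 0.92 = 13.3% | about 2.3 |
| To Day 28 | 1 − 0.70^(1/3) = 11.2% | 1 − 0.888 × 0.92 = 18.3% | 1.63 |
| To Day 84 | 30.0% | 1 − 0.70 × 0.92 = 35.6% | 1.19 |
| To about Day 168 | 1 − 0.70² = 51.0% | 1 − 0.49 × 0.92 = 54.9% | 1.08 |

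In children per group of 120, that is 22.0 against 13.5 by Day 28 (0.183 × 120 and 0.112 × 120), and 42.7 against 36.0 by Day 84.

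Varying the assumptions under the same formulas gives these risk ratios:

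| 84-day background | Added early risk | Ratio to Day 28 | Ratio to Day 84 |
|---|---|---|---|
| 10% | 5% | 2.40 | 1.45 |
| 20% | 5% | 1.65 | 1.20 |
| 30% | 5% | 1.40 | 1.12 |
| 10% | 10% | 3.80 | 1.90 |
| 20% | 10% | 2.30 | 1.40 |
| 30% | 10% | 1.79 | 1.23 |

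The direction is the same throughout; the size depends on the assumed rates.

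**Severe and related**

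If N children have an MAAE, S of them severe and R related, the number who are both lies between max(0, S + R − N) and min(S, R). With an assumed N = 12, S = 3, R = 4, the lower bound is max(0, −5) = 0 and the upper bound is 3. The separate tables are compatible with none, or with every severe case being related.

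**The case against.** The best defence is that this is an incomplete restatement and not a reversal. The time element is still in the SAP's own endpoint list, the SAP is to be read together with the protocol, and silence in 9.2.5 does not contradict protocol 7.4.3.3. That is fair as to intent. It does not supply the table or the intervals, and 9.2.6 shows that the SAP writes the time split out where one is planned.

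Several stronger readings are tempting, and the documents do not support them:

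- **Severe related events cannot be identified at all.** Not so for SAEs: the listing in 9.2.4 gives vaccination and event dates, severity and relatedness for every event. For MAAEs the statement holds for the tables; the planned listing may or may not carry these columns.
- **SAEs are diluted in 84-day totals.** The SAE window runs to Day 169/end of study, and the listing gives timing event by event.
- **Early events are hidden.** All adverse events through 28 days are tabulated by relationship (9.2.2) and by severity (9.2.3), after first vaccination and after challenge. Solicited reactions are graded over 7 days (9.1), and the overview in 9.2.1 has a row for related MAAEs. But the 28-day tables cover all adverse events and do not isolate medically attended ones, and the related-MAAE row has no time split and rests on causality judgement.
- **The trial loses power.** With 240 pooled BPZE1 recipients against 120, a 14-day window and the 30% and 8% assumptions, a two-proportion test would have 60% power, against 18% over 84 days. No MAAE test is planned and the safety summaries have no pooled BPZE1 group, so power is not the measure.

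On the joint table, the endpoint wording alone does not clearly require one, and the protocol's phrase could mean preferred terms crossed with each factor in turn. The protocol's cross-tabulation wording still supports a joint table better than the SAP's separate ones do, but this part is secondary.

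**Conclusion.** The point holds for MAAEs. The tables in SAP 9.2.5 do not deliver the time-since-vaccination part of a named secondary endpoint, the omission is undeclared, and the separate tables leave the severe-and-related count undetermined. For SAEs the gap is only a mismatch with the endpoint wording. An early MAAE excess would be diluted but not concealed, given the remaining 28-day tables. In the illustration the risk ratio falls from 1.63 at Day 28 to 1.19 at Day 84. That rests on an assumed 30% background at constant hazard and an 8% early excess, and shows direction and order of size only. This is a descriptive-reporting gap worth closing; it does not touch the primary or key secondary conclusions.

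**What to change.** In SAP 9.2.5, add that MAAEs are also summarized by treatment group and by time since the most recent study vaccination. Pre-specify the intervals and include a cumulative early window: for example through Day 14, through Day 28, then to Day 84, with children under observation as denominator. Cumulative windows matter because disjoint ones, such as Days 1–7 and 8–28, would split an excess that arises over two weeks. SAP Section 9 already separates first vaccination from the Day 85 challenge, so that needs no change.

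Also in 9.2.5, add a severity-by-relationship cross-tabulation for MAAEs. Count a child as severe and related only when the same event is both.

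In 9.2.4, add the same time wording or state that the SAE listing serves this purpose. If the sponsor prefers to leave the time split out, declare that in Section 11.

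The cost is a few extra descriptive tables from dates and classifications already collected, with some small cells.

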9.2.6. Adverse Events of Special Interest

If the COVID-19 pandemic remains ongoing in the region or if there are mass vaccinations using a COVID-19 vaccine during study conduct, any symptoms associated with COVID-19 infection or vaccination will be collected as an AESI on a unique COVID-19 eCRF through Day 169/EOS.

Subjects with SARS-CoV-2 infections as well as AESIs associated with COVID-19 infection or SARS-CoV-2 vaccine-related events will be summarized as number and percentage by SOC and PT, and by treatment groups and time since study vaccination, by severity and relationship separately.

A by-subject listing will be provided.

9.2.7. Adverse Events Leading to Study Discontinuation

TEAEs leading to study discontinuation will be summarized by SOC and PT and by treatment group.

A by-subject listing will be provided.

9.2.8. Death

TEAEs leading to death will be provided in a by-subject listing.

9.3. Clinical Laboratory Evaluations

9.3.1. Urine Pregnancy Test

For female subjects of childbearing potential who have been heterosexually active in their lifetime, a urine pregnancy test will be performed at screening and prior to any study vaccination.

Only a by-subject listing will be provided for urine pregnancy test.

9.4. Vital Sign Measurements

Vital sign measurements will include body temperature (oral, tympanic, or noncontact) and heart rate and will be collected at screening, Day 1 before vaccination and then at 30 (+30) minutes after the last study vaccination on Day 1 for all subjects, Day 85 before vaccination and then at 30 (+30) minutes after the last study vaccination for subjects in substudy, and any unscheduled visits.

If temperature is to be taken orally, the subject must not eat or drink anything hot or cold within 10 minutes prior to measurement. Temperature will also be recorded daily in a subject diary for 7

consecutive days starting the day following any study vaccination (retrospective of the highest value in the previous 24 hours).

Vital sign measurements will be summarized using descriptive statistics (mean, standard deviation, median, min, max) for reported values and change from baseline at each scheduled visit. Subjects in optional substudy will be summarized separately.

A by-subject listing will be provided.

9.5. Physical Examination

A targeted physical examination at Screening and Day 1 will include the following: head and neck (inclusive of nasal cavity and oropharynx), respiratory, cardiac, abdomen, and lymph nodes associated with the upper extremity, head, and neck. Height and weight will be measured at the Screening visit only.

Targeted physical examinations at all other timepoints will be symptom-directed and performed at the discretion of the investigator, including unscheduled visits, if necessary, to evaluate AEs.

A by-subject listing will be provided for all physical examination data.

10. Interim Analysis

An interim database analysis may occur after all subjects have completed Day 29 and sample testing for all primary and select secondary immune endpoints have been completed (mucosal and serum), but results will only be provided at treatment assignment level to maintain the blind. The site and those interacting directly with the site or subject data (eg, CRO, laboratories) will remain blinded to subject assignment until EOS or end of sample testing, depending on the activities of the associated entities.

11. Changes in the Planned Analysis

To support a rationale for immunobridging to adults, additional analyses for the age group of 10 – 17 years was added to the SAP prior to the sponsor being unblinded to subject-level data.

12. References

13. Appendices

13.1. Schedule of Events

	Screening	Treatment Period								EOS	
		All Subjects	All Subjects	Safety Lead-In Subjects ONLY	All Subjects	Subjects NOT in Substudy	Subjects Participating in Substudy ONLY ^d				
Subject Population	All Subjects	V1	S1 ^b	V2	V3 ^c	SSV 3	SSV 4	SSV 5	SSV 6	Unscheduled	EOS/Early Termination
Study Visit	Screening	V1	S1 ^b	V2	V3 ^c	SSV 3	SSV 4	SSV 5	SSV 6	Unscheduled	EOS/Early Termination
Study Day	-30 to 1 ^a	1	8	29	85	85	92	99	113	-	169
Window allowance	30	0	+3	+7	+14	+20	+3	±2	+7	-	+30
Informed consent	X					X ^{f,g}					
Inclusion/exclusion criteria	X	X ^{f,g}				X ^{f,g}					
Demographic and baseline data ^h	X										
Medical history ⁱ	X	X ^{f,g}									
Concomitant medication ^j	X	X ^g	X	X	X ^k	X ^g	X	X	X	X ^k	X ^k
Concomitant vaccines ^l	X	X ^g	X	X	X	X ^g	X	X	X	X	X
Targeted physical examination ^m	X	X ^g	X	X	X	X ^g	X	X	X	X	X
Vital sign measurements ⁿ	X	X ^g				X ^g				X	
Urine pregnancy test ^o	X	X ^g				X ^g				X	

	Screening	Treatment Period								EOS		
		All Subjects	All Subjects	Safety Lead-In Subject s ONLY	All Subjects	Subjects NOT in Substudy	Subjects Participating in Substudy ONLY ^d					
Subject Population	All Subjects						SSV 3	SSV 4	SSV 5	SSV 6	Unscheduled	
Study Visit	Screening	V1		S1 ^b	V2	V3 ^c					EOS/Early Termination	
Study Day	-30 to 1 ^a	1		8	29	85	85	92	99	113	-	169
Window allowance	30	0		+3	+7	+14	+20	+3	±2	+7	-	+30
SARS-CoV-2 test for active infection (within 72 hrs prior to vaccination) ^p		X				X						
Study vaccination ^q		X				X						
Immediate reactogenicity		X ^r				X ^r						
Subject diary dispensed ^s		X				X						
Subject diary reviewed ^t			X	X			X			X		
Nasal sampling for immunogenicity laboratory tests		X ^g		X	X	X ^g			X		X	
Mid-turbinete/nasopharyngeal sampling for B. pertussis culture or PCR			X	X ^u	X ^u		X	X				
Blood sampling for immunogenicity laboratory tests		X ^g		X	X	X			X		X	

	Screening	Treatment Period								EOS		
		All Subjects	All Subjects	Safety Lead-In Subject s ONLY	All Subjects	Subjects NOT in Substudy	Subjects Participating in Substudy ONLY ^d					
Subject Population	All Subjects						SSV 3	SSV 4	SSV 5	SSV 6	Unscheduled	
Study Visit	Screening	V1		S1 ^b	V2	V3 ^c					EOS/Early Termination	
Study Day	-30 to 1 ^a	1		8	29	85	85	92	99	113	-	169
Window allowance	30	0		+3	+7	+14	+20	+3	±2	+7	-	+30
Blood sampling for cellular-mediated Th1 and Th2 responses		X ^b		X			X ^v			X ^v		
Any TEAE (following most recent vaccination)		X		X	X		X	X	X	X	X	
Any MAAE ^w , AESI, or SAE (following first vaccination)		X		X	X	X	X	X	X	X	X	
EOS form												X

^a Screening visit may occur on Day 1 prior to study vaccination.

^b Safety lead-in subjects (only) to complete procedures listed under Study Visit S1; PBMCs to be collected in a subset of subjects.

^c Subjects not participating in the substudy are to complete procedures listed under Study Visit V3 for Day 85. Subjects in the safety lead-in cohort who are not participating in the substudy are not required to provide samples on Day 85 and may complete this visit remotely.

^d Subjects participating in the substudy (only) to complete procedures listed under Study Visits SSV3, SSV4, SSV5, and SSV6.

^e Procedures listed for an Unscheduled study visit are optional and dependent on the cause for the visit itself. An unscheduled study visit may occur at any time between enrolment and Day 169/EOS.

^f Reviewed and/or updated.

^g Performed prior to vaccination.

^h Such as date of birth (where allowed by local regulations), sex, race, ethnicity, weight, and height (with derived BMI and Z-score).

ⁱ Including prior and ongoing chronic medical conditions and past surgeries.

- j Concomitant medications will include all medications and OTC products (including herbal supplements and multivitamins) taken by the subject from the time of signing the ICF through Day 29 (and from Day 85 [following study vaccination] through Day 113 for subjects participating in the optional substudy), or through an early termination visit, if prior to these time points. The use of anti-pyrogenic medication will be specifically queried by diary during the 7 days following any study vaccination.
- k Only concomitant medications associated with any MAAE (through 84 days following any study vaccination); or AESI or SAE (through Day 169/EOS) will be recorded.
- l Vaccines received outside of the study will be specifically queried during each visit and recorded through Day 169/EOS.
- m Targeted physical examination at screening and Day 1 (prior to vaccination) to include head and neck (inclusive of nasal cavity and oropharynx), respiratory, cardiac, abdomen, and lymph nodes associated with the upper extremity, head, and neck. Targeted physical examination at all other times will be symptom-directed and performed at the discretion of the investigator. Height and weight will be measured at screening only.
- n Vital sign measurements (heart rate, body temperature) will be collected once before vaccination and then at 30 (+30) minutes after the last study vaccination (i.e., after IM vaccination on Day 1). For the safety lead-in cohort, a minimum of 30 minutes must occur between intranasal and IM vaccinations on Day 1, and medical assessment will occur prior to the second vaccination to allow for advancement. Temperature (oral or tympanic) will also be recorded daily in a subject diary for 7 consecutive days starting the day following any study vaccination (retrospective of the highest value in the previous 24 hours).
- o Female subjects of childbearing potential only who have become heterosexually active. To be performed at the discretion of the investigator based on history taking.
- p SARS-CoV-2 testing should be performed within approved national guidelines with tests that are approved through a (minimum) of emergency use authorization. Minimally invasive testing should be considered for the comfort of subjects. Subjects need to have accepted negative test results within 72 hours prior to vaccination. Repeat testing is allowed on multiple occasions. For the substudy, subjects are not considered to have a protocol violation if a retest for SARS-CoV-2 exceeds the study window.
- q On Day 1, intranasal vaccination will occur prior to IM vaccination with a minimum of 10 minutes (minimum of 30 minutes for subjects in the safety lead-in cohort of 11 to 17 year olds) between intranasal and IM vaccinations.
- r Immediate reactogenicity will be assessed at 30 minutes (+30 minutes) after the last study vaccination of the Day (i.e., after IM vaccination on Day 1, after nasal vaccination on Day 85), prior to release from clinical observation.
- s All subjects will record maximum daily reactogenicity in a subject diary for 7 consecutive days starting the day following any study vaccination (retrospective of the highest value in the previous 24 hours). Subjects will be instructed that should they have reactogenicity with a potential toxicity grade 3 at any time, they should contact the site on the same day and be seen or referred to a qualified medical facility within 24 hours.
- t Trained clinical staff will review the information from the subject diaries with the subjects and apply a standard toxicity grade (refer to Section **Error! Reference source not found.**) to any reactogenicity event. The diary will be reviewed following the first visit after vaccination for all subjects.
- u Subjects not in the safety lead-in cohort will be randomly assigned (1:1) to provide mid-turbinate/nasopharyngeal samples on either Day 29 or Day 85; however, if a subject cannot provide a sample on Day 29 (for any reason), the subject should provide a sample on Day 85 (this will not be considered a protocol deviation).
- v Collection of an extra 20 mL of blood for cellular-mediated immunity may be an option in a select number of individuals who are in the substudy (up to 45 subjects). This will not involve extra venipuncture, but only collection of additional volume.

^w Medically attended AEs will be monitored through 84 days following any study vaccination.
